The PK parameters will be assessed for the somavaratan treatment cohort only. The PD parameters are IGF-I and IGFBP-3 concentrations (GHBP and ALS as exploratory PD parameters). Sample collection for peak values of PK/PD parameters in the somavaratan treatment cohort will occur 3 ± 1 days after somavaratan dosing at 1, 3 and 9 months. Sample collection for trough values of PK/PD parameters in the somavaratan treatment cohort will occur within 3 days prior to somavaratan dosing at 6 months (sample collection prior to dosing) and at the end of the dosing interval at 12 months. Sample collection for PD parameters in the daily rhGH group will occur at each in-clinic visit (Day 1, and at 1, 3, 6, 9, and 12 months).

Descriptive PK parameters (somavaratan concentrations) and PD parameters (IGF-I, IGFBP-3, GHBP and ALS) will be determined. For each subject, IGF-I C_{max} and change from baseline will also be compared to age-and gender specific normative data and expressed as both concentrations and standard deviation scores (SDS).

Efficacy

The primary efficacy endpoint for this study is annual height velocity (cm/yr) in the first year (12 months) of treatment.

Secondary efficacy endpoints include: changes in height standard deviation score, bone age relative to chronological age (BA/CA), body mass index, body weight, IGF-I, IGFBP-3 and pubertal staging.

Study Population:

The study population will consist of naïve to treatment, pre-pubertal children with growth hormone deficiency (GHD). A 3:1 randomization ratio will be used for the somavaratan treatment cohort and the daily rhGH treatment cohort, respectively. Screening and randomizations will continue until a minimum of approximately 84 subjects have been enrolled or enrollment has been completed based on the sample size re-estimation procedure.

CRITERIA FOR INCLUSION AND EXCLUSION

Inclusion Criteria:

1. Chronological Age ≥ 3.0 years and ≤ 10.0 (girls) and ≤ 11.0 (boys).
2. Pre-pubertal status: Absent breast development in girls, testicular volume <4.0 mL in boys.
3. Diagnosis of GHD as documented two or more GH stimulation test results ≤ 10.0 ng/mL. The use of prior GH stimulation test results is permitted providing the

stimulatory agents, GH assay and test result are approved in writing by the medical monitor.

4. Height SDS \leq -2.0 at screening.
5. Weight for Stature \geq 10th percentile.
6. IGF-I SD score \leq -1.0 at screening.

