6.3 Physical Examination

A physical examination will be performed during Screening and at Months 6 and 12. Brief physical examinations are directed at reported health complaints and will be performed at Day 1 and Months 1, 3, and 9. Injection sites will be examined at all in clinic visits.

Pubertal staging will be performed during Screening and at Months 6 and 12. The method of Tanner and Marshall will be used to assess breast and pubic hair development.^{28,29} For males, testicular volume will be estimated by palpation with reference to a Prader orchidometer.

Ocular fundoscopy through undilated pupil by the PI, sub-investigator, or ophthalmologist will be conducted to detect signs of intracranial hypertension or retinopathy at Screening. At all sites same day fundoscopy is required as clinically indicated if the subject exhibits signs and symptoms of intracranial hypertension (e.g., severe or prolonged headache lasting more than 12 hours or visual disturbances lasting more than 2 hours). Immediate medical attention is required for subjects who develop signs and symptoms of intracranial hypertension.

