All subjects will return to the clinic at the end of Month 9 for an assessment and blood sample collection. For subjects in the somavaratan treatment cohort, this visit will occur 3 ± 1 days after somavaratan dosing (peak sample collection). Assessments on Visit Month 9 include:

1. Brief physical exam (brief, problem-specific exam may be performed for any reported AE at the discretion of the investigator).
2. Ocular fundoscopy through undilated pupils to detect signs of intracranial hypertension or retinopathy (may be conducted by the PI or sub-investigator). North America sites only.
3. Vital signs including respiratory rate, body temperature, pulse rate, and systolic/diastolic blood pressure taken after 5 minutes rest in a sitting position.
4. Height measured without shoes in triplicate by stadiometer.
5. Body weight measured in light clothing and without shoes.
6. Collection of blood samples for PD (IGF-I, IGFBP-3), PK, (somavaratan concentration in the somavaratan treatment cohort only) and immunogenicity.
7. Recording of AEs using the CTCAE grading scale.
8. Recording of all concomitant medications.
9. Scheduling of study doses and next clinic visit. Distribution of DP and ancillary supplies to parent/guardian that will be required for at home dosing events.
10. Reminder that used and partially used somavaratan DP vials or daily rhGH DP must be returned to clinic at next visit.
11. Dose programming (based on subject weight) of ePRO solution and review of dosing documentation instructions with parent/guardian.
12. Return of used and partially used vials by parent/guardian for accountability.

7.2.6 *Visit Month 12 Procedures*

All subjects will return to the clinic at the end of Month 12 for an assessment and collection of blood samples. For subjects in the somavaratan treatment cohort, this visit will occur 15 ± 1 days after the last somavaratan dosing (trough sample collection). Assessments on Visit Month 12 include:

1. Physical exam.
2. Ocular fundoscopy through undilated pupils to detect signs of intracranial hypertension or retinopathy (may be conducted by the PI or sub-investigator). North America sites only.
3. Tanner staging of pubic hair for boys and girls, breast development for girls and estimated testicular volume by orchidometer for boys.
4. Vital signs including respiratory rate, body temperature, pulse rate, and systolic/diastolic blood pressure taken after 5 minutes rest in a sitting position.

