Appendix 1 Schedule of Events for Somavaratan Subjects

Activity/Assessment	Screening	Day 1	Month 1 ¹	Month 3 ¹	Month 6 ¹	Month 9 ¹	Month 12 ²
Informed Consent/Assent ³	X						
Inclusion/Exclusion Criteria	X						
Medical History	X						
Physical Exam	X				X		X
Brief Physical Exam ⁴		X	X	X		X	
Fundoscopy	X	X	X	X	X	X	X
Pubertal Staging ⁶	X				X		X
Vital Signs ⁷	X	X	X	X	X	X	X
12-lead ECG ⁸	X			X			
Height ⁹ , Weight ¹⁰	X	X	X	X	X	X	X
PK/PD Samples ¹¹	X	X	X	X	X	X	X
GHBP and ALS		X	X		X		X
Antibody Samples ¹²	X		X	X	X	X	X
Adrenal Assessment ¹³	X						
Hematology ¹⁴	X		X		X		X
Chemistry ¹⁵	X		X		X		X
Hemoglobin A1c	X		X		X		X
Free T4, TSH	X		X		X		X
Urinalysis ¹⁶	X		X		X		X
Bone Age ¹⁷	X						X
Adverse Events ¹⁸		X	X	X	X	X	X
Concomitant Medications	X	X	X	X	X	X	X
Somavaratan Dosing ¹⁹		X					

1. For Month 1, 3 and 9, the visits will occur 3 ± 1 days after a somavaratan dose (peak sample collection). For Month 6, the visit will occur 15 ± 1 days after somavaratan dosing (trough sample collection).
2. Should occur after the end of the last dosing interval and approximately 12 months after the Day 1 visit.
3. Informed consent to be completed by duly authorized subject representative. Assent provided by subject, where required.
4. A directed physical exam to address health complaints and to examine injection sites.
5. Ocular fundoscopy through undilated pupil will be conducted by the PI, sub-investigator, or ophthalmologist to detect signs of intracranial hypertension or retinopathy. In sites outside North America, protocol-required fundoscopy will be conducted at screening. At all sites same day fundoscopy is required as clinically indicated if the subject exhibits signs and symptoms of intracranial hypertension (e.g., severe or prolonged headache lasting more than 12 hours or visual disturbances lasting more than 2 hours). Immediate medical attention is required for subjects who develop signs and symptoms of intracranial hypertension.
6. Tanner staging of pubertal hair (boys and girls), breast development (girls) and estimated testicular volume by orchidometer (boys).
7. Includes temperature, respiratory rate, pulse rate and systolic/diastolic blood pressure taken after 5 minutes rest in a sitting position.
8. All subjects will receive 12-lead ECGs (triplicate tracings) at Screening and Month 3.
9. Heights to be measured without shoes in triplicate by stadiometer. Stadiometer should be calibrated just before use. Required precision ≤ 0.2 cm.

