Relationship and severity of adverse events will be summarized (subject count, % of subjects) for each treatment group. For these summaries, multiple occurrences of an event within a subject will be classified as a single observation with the strongest relationship and maximum severity ratings. In addition, frequency tables of all reported events with each associated relationship and severity will be presented.

A tabulation of the incidence of all Grade 3 and 4 treatment-emergent adverse events will be displayed, overall and those related to study drug. Furthermore, a tabulation of the incidence of all treatment-emergent injection site adverse events will be created including, but not limited to, events such as pain/tenderness, erythema, lipoatrophy, stinging, burning, itching, etc. A listing of the treatment-emergent injection site adverse events will supplement the tabulation and will contain dosing information including but not limited to, onset time since last dose, relationship to study drug, dose, grade, injection location, injection volume, number of injections received per dosing event, and duration.

Moreover, a listing of instances of headache reported as an adverse event will be presented which will include information about the event such as, but not limited to, onset time since last dose, relationship to study drug, dose, grade, and duration.

Serious Adverse Events (SAE) are defined as those events that are life threatening, require hospitalization or prolong existing hospitalization; or cause disability, incapacity, or death; or require intervention to prevent such outcomes. These events will be classified as SAEs by the Investigator and appropriate medical review and will be summarized by treatment group, as well as total subjects exposed.

A listing of SAE data will be provided to supplement the tabulated results.

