6.13.2 Physical Exams

For the complete physical examinations performed, the proportion of subjects reporting results of “Normal”, “Abnormal, Not Clinically Significant,” and “Abnormal, Clinically Significant” will be calculated and presented for each scheduled time point, body system and treatment group. Any changes in physical examinations post-injection, including injection site findings, will be captured as an AE and will be presented in those tabulations and/or listings. The proportion of subjects that report changes in brief physical examination (e.g., change/no change) will be calculated and presented by treatment group across visits.

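### Injection sites are inspected 2-4 or 14-16 days after a somavaratan dose but about a day after an rhGH dose, so transient visible reactions found only by inspection may be under-recorded on somavaratan

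*Protocol*

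**What the plan says.** **Inspection.** Protocol 6.3 applies to both arms: "Injection sites will be examined at all in clinic visits".

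**Somavaratan visits are dose-linked.** Protocol Appendix 1, footnote 1, says "For Month 1, 3 and 9, the visits will occur 3 ± 1 days after a somavaratan dose (peak sample collection" and "For Month 6, the visit will occur 15 ± 1 days after somavaratan dosing (trough sample collection"; the SAP 3.2.1 schedule repeats both. For Month 12, protocol 7.2.6 says "this visit will occur 15 ± 1 days after the last somavaratan dosing (trough sample collection". The synopsis words Month 6 differently: trough sampling "will occur within 3 days prior to somavaratan dosing at 6 months".

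**rhGH visits are not dose-linked.** rhGH is given once daily (protocol 5.3). Protocol Appendix 2 and SAP 3.2.2 give no visit window relative to the dose.

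**From finding to AE table.** SAP 6.13.2: "Any changes in physical examinations post-injection, including injection site findings, will be captured as an AE". SAP 6.13.1: "a tabulation of the incidence of all treatment-emergent injection site adverse events will be created". SAP 6.13.1 also plans a listing of these events with onset time since the last dose and duration.

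**Other relevant rules.** AEs are collected at each clinic visit (protocol 6.8.1), and any sign or symptom after the first dose counts (SAP 6.13.1). Protocol 6.8.6 makes an examination finding an AE only if the PI judges it clinically significant or otherwise important, or if it leads to withdrawal or treatment. The ePRO records time, date, volume and site of each dose (protocol 5.7); no site-reaction item is listed.

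**The concern.** A reaction that has faded before the visit cannot be found by inspection. The visit schedule, set for PK/PD sampling, puts a gap of at least two days between a somavaratan injection and any scheduled inspection, while a child on daily rhGH nearly always has a fresh site to look at. The same transient sign therefore has different chances of being found in the two arms, and the SAP places what is found in the same incidence table as reported events.

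Comparing safety is part of the primary objective. Protocol Table 7 lists seven injection-site terms among related AEs in 68 children on somavaratan. Several are visible signs: erythema 8 (11.8%), hematoma 1 (1.5%) and hemorrhage 1 (1.5%). Protocol 6.8.5 describes somavaratan AEs as mostly mild and transient, which is the kind this schedule can miss. Neither document mentions the difference in inspection timing.

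**Working it through.** The documents give no figure for this point, so there is none to reproduce.

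**Step 1: time from last dose to inspection**

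- Somavaratan, Months 1, 3, 9: 3 ± 1 = 2 to 4 days.
- Somavaratan, Months 6, 12: 15 ± 1 = 14 to 16 days.
- Somavaratan, Month 6 as worded in the synopsis: doses are 15 ± 2 = 13 to 17 days apart, less 0 to 3 days, so 10 to 17 days. This does not match 14 to 16 exactly, but it does not change the conclusion.
- rhGH, all visits: about 1 day, inferred from daily dosing.
- Day 1: the examination is item 1 and dosing item 11 (protocol 7.2.1), with no later inspection listed. Month 6 allows optional in-clinic dosing after blood sampling (protocol 7.2.4), again with no inspection listed afterwards.

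**Step 2: visits at which a sign from the last dose is still visible**

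Assume a sign lasts D days and is visible if the time since the dose is at most D. Assume the days within each window are equally likely. There are three visits at 2, 3 or 4 days and two at 14, 15 or 16 days.

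| D (days) | Somavaratan, of 5 visits | rhGH, of 5 visits |
|---|---|---|
| 1 | 0 | 5 |
| 2 | 3 × 1/3 = 1.0 | 5 |
| 3 | 3 × 2/3 = 2.0 | 5 |
| 4 to 7 | 3 × 1 = 3.0 | 5 |
| 14 | 3 + 2 × 1/3 = 3.7 | 5 |
| 16 | 5 | 5 |

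**Step 3: effect on recorded incidence**

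Assumptions, none from the documents: 30% of children in each arm have such a reaction; an affected child reacts to any one injection with probability q, independently; a share s of affected children is captured by report whatever inspection shows.

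Recorded incidence = 30% × [s + (1 − s) × d], where d is the chance of being found at one or more of the five visits:

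- Somavaratan: d = 1 − product over the five visits of (1 − q × v), where v is the chance that the sign is visible at that visit.
- rhGH: d = 1 − (1 − q)^(5D), because D daily injections are in view at each visit.

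Examples at q = 0.5:

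- D = 1: somavaratan d = 0; rhGH d = 1 − 0.5^5 = 0.969, and 30% × 0.969 = 29.1%.
- D = 4: somavaratan d = 1 − 0.5^3 = 0.875, and 30% × 0.875 = 26.2%.

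Recorded incidence, somavaratan vs rhGH:

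| D, q | s = 0 | s = 0.5 | s = 0.9 |
|---|---|---|---|
| 1 day, 0.5 | 0.0% vs 29.1% | 15.0% vs 29.5% | 27.0% vs 29.9% |
| 1 day, 0.1 | 0.0% vs 12.3% | 15.0% vs 21.1% | 27.0% vs 28.2% |
| 2 days, 0.5 | 12.6% vs 30.0% | 21.3% vs 30.0% | 28.3% vs 30.0% |
| 4 days, 0.5 | 26.2% vs 30.0% | 28.1% vs 30.0% | 29.6% vs 30.0% |
| 16 days, 0.5 | 29.1% vs 30.0% | 29.5% vs 30.0% | 29.9% vs 30.0% |
| 16 days, 0.1 | 12.3% vs 30.0% | 21.1% vs 30.0% | 28.2% vs 30.0% |

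At s = 1 both arms record 30.0% in every row. In the 16-day rows the time since dose hides nothing (5 of 5 visits in both arms). The gap left there, large at q = 0.1, arises because 16 daily injections are in view at an rhGH visit against one on somavaratan. That is dosing frequency, not inspection timing. A finding lasting months is still present at the next visit in either arm.

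**Step 4: the two AE rules side by side**

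Protocol 6.8.6 filters examination findings through the PI's judgment of importance. SAP 6.13.2 has no filter. SAP section 1 says that the SAP's analyses prevail where they differ from the protocol and that differences are described in SAP 6.2. The list in 6.2 does not mention this one, and the clause covers analyses, not what sites record. How many inspection findings reach the AE table thus depends on which rule a site follows.

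**The case against.** Inspection is only one route into the AE table. AEs are also collected by report at every visit, in the same months in both arms. Most injection-site terms named in SAP 6.13.1 (pain or tenderness, stinging, burning, itching) are symptoms, which need no visible site. Pain, the commonest related event in protocol Table 7 (39 of 68, 57.4%), is one of them, so that figure does not show what is at stake here; erythema at 11.8% is the more relevant one. Under protocol 6.8.6, trivial redness would often not become an AE at all. The order of the Day 1 list is not stated to be chronological, and nothing stops staff recording a reaction to a dose given in clinic. The comparison is descriptive, with no formal safety test planned, and the listing already shows onset time and duration.

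Most of this stands, and it limits the point to transient visible signs found only by inspection. It does not remove it. Reports of mild redness depend on recall over visits up to three months apart. The listing does not separate inspected from reported events, and neither does the incidence table. A descriptive table can also mislead if the arms are observed differently.

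A reader might go further and compute 1 − (1 − q)^5 for q = 5%, 10% and 20% per injection, setting 23%, 41% and 67% of rhGH children against 0% on somavaratan. The documents do not support that as the size of the problem. The zero follows from assuming that every reaction lasts under two days, for which no duration is given, and reported events are left out. With the 24 assigned somavaratan doses of protocol Table 1 and independent injections, the same q would mean that 1 − (1 − q)^24, about 71%, 92% and 99.5% of somavaratan children, truly had a reaction; with 365 doses it is about 100% on rhGH. Inspection would then miss many affected children in both arms.

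**Conclusion.** The difference in inspection timing is established for somavaratan by the stated windows, and for rhGH by a fair inference from daily dosing. For transient visible signs found only by inspection, it works towards under-recording on somavaratan relative to rhGH. In the illustration for one-day signs, the gap runs from nearly the whole incidence to nil as reporting rises from none to complete; at 90% reporting and q = 0.5 it is 2.9 percentage points (29.9 − 27.0). Those figures rest on assumed duration, reaction frequency and reporting.

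A reader might infer that the injection-site comparison as a whole is biased in favour of somavaratan. The documents do not support that. Reported symptoms and persistent findings are little affected by when the site is inspected. In an open-label trial, closer attention to the new product could also push reporting the other way. Net direction and size cannot be determined from the documents. The primary efficacy test is not touched.

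The mismatch between protocol 6.8.6 and SAP 6.13.2 is a separate, firm finding and needs no assumption.

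**What to change.** 1. In SAP 6.13.1, keep the all-events injection-site incidence table. Add a supplementary table by arm showing incidence with and without events first found only by clinic inspection. The version without them does not depend on when the inspection fell.
2. In the same table or beside it, tabulate inspection findings by days since the last injection, using the dose dates already in the ePRO.
3. Reconcile protocol 6.8.6 with SAP 6.13.2 on which injection-site findings become AEs, and record the outcome in SAP 6.2 if the documents are to differ.
4. Reconcile the synopsis wording for Month 6 trough sampling with the window in protocol 7.2.4 and Appendix 1.

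Cost: one extra table and, if the CRF does not record how an event was found, one source field. No visit is added or moved.

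Two alternatives are weaker. Basing the main incidence on parent-reported events alone would drop genuine observed findings and depart from the SAP's own AE definition. A site-reaction question at each ePRO dose entry would be asked about 365 times in one arm and 24 in the other, creating a new imbalance in per-child incidence.

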6.4 Vital Signs

Vital signs, height and weight are measured at the beginning of all in clinic visits.

Pulse rate, respiration rate, body temperature, and systolic/diastolic blood pressure will be measured with the subject sitting quietly for at least five minutes.

Height will be measured, in triplicate, using a wall-based stadiometer. The stadiometer should be calibrated just prior to use. The subject will be measured without shoes. Required precision of repeat height measurements is 0.2 cm (2 mm).

Weight will be measured with subject wearing light clothing and without shoes.

6.5 **Electrocardiograms (ECGs)**

ECGs will be conducted using 12-lead ECG equipment at Screening and repeated at Month 3 (at the expected time of somavaratan C_{max}). Triplicate tracings required.

6.6 **Clinical Laboratory Tests**

6.6.1 *Laboratory Parameters*

Subjects will be in a seated or supine position during blood collection. Urine tests will be performed locally. Clinical laboratory tests will be conducted by a central laboratory to be identified by the Sponsor and include the following:

Table 3 List of Laboratory Tests

Hematology: – Red blood cell (RBC) count – White blood cell (WBC) with differential – Platelet count – Hemoglobin (Hgb) – Hematocrit (Hct) – Mean corpuscular hemoglobin (MCH) – Mean corpuscular hemoglobin concentration (MCHC) – Mean corpuscular volume (MCV)	Serum Chemistry: – Albumin (ALB) – Alkaline phosphatase (ALK-P) – Alanine aminotransferase (ALT; SGPT) – Aspartate aminotransferase (AST; SGOT) – Blood urea nitrogen (BUN) – Calcium (Ca) – Creatinine – Gamma-glutamyl transpeptidase (GGT) – Phosphate – Potassium (K) – Sodium (Na) – Total protein
Urinalysis: Performed locally by Urine Multistix® (or similar) – Bilirubin – Glucose – Ketones – Nitrite – Occult blood – pH – Protein – Urobilinogen	Pharmacodynamics: – IGF-I – IGFBP-3 – GHBP – ALS Immunogenicity: – Anti-drug antibodies (ADA) detection and characterization
Endocrine: – Glucose – HbA1c – Free T4 – TSH – Cortisol ¹	Pharmacokinetics: – somavaratan plasma concentration

1: Repeat adrenal testing in symptomatic/suspicious subjects as needed

6.6.2 *Sample Collection, Storage, and Shipping*

The safety, pharmacokinetic and pharmacodynamics assessments require blood samples to be collected during the study. The total blood volume required to be collected over the course of the study including the screening visit has been minimized and is provided in Table 4.

Table 4 Maximum Blood Volumes Required

Sample Type	Blood Volume (mL) per Sample	Collection Schedule							Total Number of Occasions	Total Per Subject (mL)
		Screening	Day 1	M1	M3	M6	M9	M12		
Hematology	2.0	X		X		X		X	4	8.0
Chemistry	4.0	X		X		X		X	4	16.0
PD ¹	4.0	X	X	X	X	X	X	X	7	28.0
PK ²	2.0		X	X	X	X	X	X	6	12.0
Antibodies	3.0	X		X	X	X	X	X	6	18.0
HbA1c	2.0	X		X		X		X	4	8.0
Total Blood Volume (mL) Required For Study									90.0	

1: May include IGF-I, IGFBP-3, GHBP and ALS (refer to Appendix 1)

2: PK collected in the somavaratan treatment cohort only

To ensure subject safety, no more than 17 mL (and not to exceed 2 mL/kg) of blood will be collected from individual subjects at any specific time point and will not exceed 4 mL/kg in any 30-day blood collection period.

